#### An SAE is defined as any untoward medical occurrence that, at any dose:

#### 1. Results in death

#### 2. Is life-threatening

The term "life-threatening" in the definition of "serious" refers to an event in which the participant was at risk of death at the time of the event. It does not refer to an event, which hypothetically might have caused death, if it was more severe.

#### 3. Requires inpatient hospitalization or prolongation of existing hospitalization

In general, hospitalization signifies that the participant has been detained (usually involving at least an overnight stay) at the hospital or emergency ward for observation and/or treatment that would not have been appropriate in the physician's office or outpatient setting. Complications that occur during hospitalization are AEs. If a complication prolongs hospitalization or fulfills any other serious criteria, the event is serious. When in doubt as to whether "hospitalization" occurred or was necessary, the AE should be considered serious.

Hospitalization for elective treatment of a pre-existing condition that did not worsen from baseline is not considered an AE.

#### 4. Results in persistent disability/incapacity

- The term disability means a substantial disruption of a person's ability to conduct normal life functions.
- This definition is not intended to include experiences of relatively minor medical significance such as uncomplicated headache, nausea, vomiting, diarrhea, influenza, and accidental trauma (eg, sprained ankle) which may interfere with or prevent everyday life functions but do not constitute a substantial disruption.

#### 5. Is a congenital anomaly/birth defect

#### 6. Other situations:

• Medical or scientific judgment should be exercised in deciding whether SAE reporting is appropriate in other situations such as important medical events that may not be immediately life-

#### An SAE is defined as any untoward medical occurrence that, at any dose:

threatening or result in death or hospitalization but may jeopardize the participant or may require medical or surgical intervention to prevent one of the other outcomes listed in the above definition. These events should usually be considered serious.

• Examples of such events include invasive or malignant cancers, intensive treatment in an emergency room or at home for allergic bronchospasm, blood dyscrasias or convulsions that do not result in hospitalization, or development of drug dependency or drug abuse.

#### A SUSAR is defined as:

An event that is assessed as serious by the Investigator and/or Alexion that is not listed in the appropriate Reference Safety Information (IB) and has been assessed that there is at least a reasonable possibility that the event is related to the study intervention by the Investigator and/or Alexion.

Alexion has procedures that will be followed for the recording, medical assessment, and expedited reporting of SUSARs that are consistent with global regulations, legislation, and guidance documents.

Suspected unexpected serious adverse reactions will undergo expedited reporting to the national regulatory authorities, IRBs/IECs, and Investigators following local regulatory reporting requirements where applicable.

#### **10.3.3.** Recording and Follow-Up of AE and/or SAE

#### **Recording of AE and/or SAE**

- When an AE/SAE occurs, it is the responsibility of the Investigator to review all documentation (eg, hospital progress notes, laboratory reports, and diagnostics reports) related to the event.
- The Investigator will then record all relevant AE/SAE information in the eCRF.
- It is not acceptable for the Investigator to send photocopies of the participant's medical records to Alexion in lieu of completion of the Alexion AE/SAE eCRF page.
- There may be instances when copies of medical records for certain cases are requested by Alexion. In this case, all participant identifiers, with the exception of the participant number, will be redacted on the copies of the medical records before submission to Alexion.
- The Investigator will attempt to establish a diagnosis of the event based on signs, symptoms, and/or other clinical information. Whenever possible, the diagnosis (not the individual signs/symptoms) will be documented as the AE/SAE.

#### **Assessment of Intensity**

The Investigator will make an assessment of intensity for each AE and SAE reported during the study and assign it to one of the following categories from National Cancer Institute CTCAE v5.0, published 27 Nov 2017:

- Grade 1: Mild (awareness of sign or symptom, but easily tolerated)
- Grade 2: Moderate (discomfort sufficient to cause interference with normal activities)
- Grade 3: Severe (incapacitating, with inability to perform normal activities)
- Grade 4: Life-threatening
- Grade 5: Fatal

#### **Recording of AE and/or SAE**

An event is defined as "serious" when it meets at least one of the predefined outcomes as described in the definition of an SAE, not when it is rated as severe.

#### Assessment of Causality

- The Investigator is obligated to assess the relationship between the study intervention and each occurrence of each AE or SAE. An Investigator causality assessment must be provided for all AEs (both nonserious and serious). This assessment must be recorded in the eCRF and on any additional forms, as appropriate. The definitions for the causality assessments are as follows:
  - Not related: There is no reasonable possibility the study intervention caused the AE.

- The AE has a more likely alternative etiology; it may be due to underlying or concurrent illness, complications, concurrent treatments, or effects of another concurrent drug.

- The event does not follow a reasonable temporal relationship to administration of the study intervention.

- Related: There is a reasonable possibility the study intervention caused the AE.

- The AE has a temporal relationship to the administration of the study intervention.

- The event does not have a likely alternative etiology.

- The event corresponds with the known pharmaceutical profile of the study intervention.

- There is improvement on discontinuation and/or reappearance on rechallenge.

- The Investigator will use clinical judgment to determine the relationship.
- Alternative causes, such as underlying disease(s), concomitant therapy, and other risk factors, as well as the temporal relationship of the event to study intervention administration will be considered and investigated.
- The Investigator will also consult the IB and/or Product Information, for marketed products, in his/her assessment.
- For each AE/SAE, the Investigator **must** document in the medical notes that he/she has reviewed the AE/SAE and has provided an assessment of causality.
- There may be situations in which an SAE has occurred, and the Investigator has minimal information to include in the initial report to Alexion. However, it is very important that the Investigator always make an assessment of causality for every event before the initial transmission of the SAE data to Alexion.
- The Investigator may change his/her opinion of causality in light of follow-up information and send an SAE follow-up report with the updated causality assessment.
- The causality assessment is one of the criteria used when determining regulatory reporting requirements.

#### Follow-up of AEs and SAEs

• The Investigator is obligated to perform or arrange for the conduct of supplemental measurements and/or evaluations as medically indicated or as requested by Alexion to elucidate

#### Follow-up of AEs and SAEs

the nature and/or causality of the AE or SAE as fully as possible. This may include additional laboratory tests or investigations, histopathological examinations, or consultation with other health care professionals.

- If a participant dies during participation in the study or during a recognized follow-up period, the Investigator will provide Alexion with a copy of any postmortem findings including histopathology.
- New or updated information will be recorded in the originally completed eCRF.
- The Investigator will submit any updated SAE data to Alexion within 24 hours of receipt of the information.

## 10.3.4. Reporting of SAEs

#### SAE Reporting to Alexion via an Electronic Data Collection Tool

- 1. All SAEs will be recorded and reported to Alexion immediately and within 24 hours of awareness.
- 2. The primary mechanism for reporting an SAE to Alexion will be the EDC system.
- 3. If the electronic system is unavailable or site staff is unable to process the SAE via the EDC system at the time that the Investigator or site becomes aware of an SAE, the site will use the paper Contingency Form for SAE Reporting via facsimile or email. Facsimile transmission or email may also be used in the event of electronic submission failure.
  - Email: [contact] or Fax: [name]
- 4. The site will enter the SAE data into the EDC system as soon as it becomes available.
- 5. When further information becomes available, the EDC should be updated immediately with the new information and an updated SAE report should be submitted to Alexion Global Drug Safety (GDS) within 24 hours of Investigator/site awareness.
- 6. After the participant has completed the study, no new data or changes to existing data are expected to be entered in the EDC system.
  - a. If a site receives a report of a new SAE from a study participant which the Investigator considers to be related to the study intervention, or the site receives updated data on a previously reported SAE after the EDC system has been taken offline, then the site can report this information on a paper Contingency Form for SAE Reporting via facsimile or email.

## 10.3.5. Unexpected Events

Apart from the reporting of SUSARs, there may be other events which are relevant in terms of benefit-risk balance and which should be reported in a timely manner according to regional and national requirements. It is important for participant safety that, in addition to SAEs and reactions, all unexpected events that might materially influence the benefit-risk assessment of the study intervention or that would lead to changes in the administration of the study intervention or in overall conduct of a clinical trial should be reported. Examples of such unexpected events include an increase in the rate of occurrence of expected serious adverse reactions which may be clinically important, a significant hazard to the patient population, such as lack of efficacy of a medicinal product, or a major safety finding from a newly completed animal study (such as, carcinogenicity).

Under the EU CTR 536/2014 (49), where unexpected events require an urgent modification of a clinical trial, it should be possible for Alexion and the Investigator to take urgent safety measures without awaiting prior authorization. If such measures constitute a temporary halt of the clinical trial, Alexion should apply for a substantial modification before restarting the clinical trial.

## **10.4.** Medication Error, Drug Abuse, and Drug Misuse

## **Medication Error**

For the purposes of this clinical study a medication error is an unintended failure or mistake in the treatment process for an IMP or Alexion AxMP that either causes harm to the participant or has the potential to cause harm to the participant.

Any events of medication error, with or without associated AEs, are to be captured and forwarded to Alexion Global Patient Safety via email or facsimile ([contact] or [contact]) using the Alexion Clinical Study Medication Error Report Form.

A medication error is not lack of efficacy of the drug, but rather a human or process related failure while the drug is in control of the study site staff or participant.

Medication error includes situations where an error:

- Occurred
- Was identified and intercepted before the participant received the drug
- Did not occur, but circumstances were recognized that could have led to an error

Examples of events to be reported in clinical studies as medication errors:

- Drug name confusion
- Dispensing error, eg, medication prepared incorrectly, even if it was not actually given to the participant
- Drug not administered as indicated, eg, wrong route or wrong site of administration
- Drug not taken as indicated, eg, tablet dissolved in water when it should be taken as a solid tablet
- Drug not stored as instructed, eg, kept in the refrigerator when it should be at room temperature
- Wrong participant received the medication (excluding IRT/Randomization and Trial Supply Management [RTSM] errors)
- Wrong drug administered to participant (excluding IRT/RTSM errors)

Examples of events that **do not** require reporting as medication errors in clinical studies:

- Errors related to or resulting from IRT/RTSM including those which led to one of the above listed events that would otherwise have been a medication error
- Participant accidentally missed drug dose(s), eg, forgot to take medication
- Accidental overdose (will be captured as an overdose, see Section 8.4)
- Participant failed to return unused medication or empty packaging

Medication errors are not regarded as AEs but AEs may occur as a consequence of the medication error.

## Drug Abuse

For the purpose of this study, drug abuse is defined as the persistent or sporadic intentional, non-therapeutic excessive use of IMP or Alexion AxMP for a perceived reward or desired non-therapeutic effect.

Any events of drug abuse, with or without associated AEs, are to be captured and forwarded to Alexion Global Patient Safety via email or facsimile ([contact] or [name]) using the Alexion Clinical Study Drug Misuse or the Drug Abuse Form. This form should be used both if the drug abuse happened in a study participant or if the drug abuse involves a person not enrolled in the study (such as a relative of the study participant).

Examples of drug abuse include but are not limited to:

- The drug is used with the intent of getting a perceived reward (by the study participant or a person not enrolled in the study)
- The drug in the form of a tablet is crushed and injected or snorted with the intent of getting high

## **Drug Misuse**

Drug misuse is the intentional and inappropriate use of IMP or Alexion AxMP for medicinal purposes outside of the authorized product information, or for unauthorized IMPs or Alexion AxMPs, outside the intended use as specified in the protocol, including deliberate administration of the product by the wrong route.

Events of drug misuse, with or without associated AEs, are to be captured and forwarded to Alexion Global Patient Safety via email or facsimile ([contact] or [name]) using the Alexion Clinical Study Drug Misuse or Drug Abuse Report Form. This form should be used both if the drug misuse happened in a study participant or if the drug misuse involves a person not enrolled in the study (such as a relative of the study participant).

Examples of drug misuse include but are not limited to:

- The drug is used with the intention to cause an effect in another person
- The drug is sold to other people for recreational purposes
- The drug is used to facilitate assault in another person
- The drug is deliberately administered by the wrong route
- The drug is split in half because it is easier to swallow, when it is stated in the protocol that it must be swallowed whole
- Only half the dose is taken because the study participant feels that he/she is feeling better when not taking the whole dose
- Someone who is not enrolled in the study intentionally takes the drug

## **10.5.** Contraceptive Guidance and Collection of Pregnancy Information

## 10.5.1. Definitions

## Woman of Childbearing Potential (WOCBP)

A woman is considered fertile following menarche and until becoming postmenopausal unless permanently sterile (see below).

If fertility is unclear (eg, amenorrhea in adolescents or athletes) and a menstrual cycle cannot be confirmed before first dose of study intervention, additional evaluation should be considered.

## Women in the Following Categories Are Not Considered WOCBP

- 1. Premenarchal
- 2. Premenopausal female with one of the following:
  - Documented hysterectomy
  - Documented bilateral tubal ligation or bilateral salpingectomy
  - Documented bilateral oophorectomy

For individuals with permanent infertility due to an alternate medical cause other than the above, (eg, Mullerian agenesis, androgen insensitivity), Investigator discretion should be applied to determining study entry.

Note: Documentation can come from the site personnel's review of the participant's medical records, medical examination, or medical history interview.

- 3. Postmenopausal female
  - A postmenopausal state is defined as no menses for 12 months without an alternative medical cause prior to the Day 1 Visit.
    - A high FSH level in the postmenopausal range may be used to confirm a
      postmenopausal state in women not using hormonal contraception or HRT.
      However, in the absence of 12 months of amenorrhea, confirmation with more
      than one FSH measurement may be required. In the absence of 12 months of
      amenorrhea the reason for not obtaining FSH levels should be documented by the
      Investigator at the time of the Screening Visit.
  - Females on HRT and whose menopausal status is in doubt will be required to use one of the non-estrogen hormonal highly effective contraception methods if they wish to continue their HRT during the study. Otherwise, they must discontinue HRT to allow confirmation of postmenopausal status before study enrollment.
- 4. Permanent sterilization at least 6 weeks prior to the Day 1 Visit.

## **10.5.2.** Contraception Guidance

Contraceptive use by male or female participants should be consistent with local regulations regarding the methods of contraception utilized for those participating in clinical studies. If teratogenic effects are suspected to be transferred to a fetus/embryo from a female spouse/partner

of a male participant, pregnancy follow-up information will be obtained for the partner who becomes pregnant (refer to Section 10.5.3.1). In these cases, follow-up will be conducted on the pregnant partner in the same manner as a female participant who becomes pregnant during the study.

## 10.5.2.1. Guidance for Female Participants

Female participants of childbearing potential must have a negative serum pregnancy test as required by local regulations at the Screening Visit and a negative urine pregnancy test before the first dose of study intervention on Day 1. Additional requirements for pregnancy testing during and after dosing with study intervention are indicated in the SoAs (Table 2, Table 3, and Table 4).

The Investigator is responsible for the review of medical history, menstrual history, and recent sexual activity to decrease the risk for inclusion of a woman with an early undetected pregnancy.

The Investigator should evaluate the potential for contraceptive method in relationship to the first dose of study intervention.

Female participants of childbearing potential must use a highly effective method of contraception, including at least 1 of the following until at least 30 days after the final dose of study intervention.

- 1. Intrauterine device in place for at least 6 weeks prior to first dose of study intervention.
- 2. Progestogen-only hormonal contraception associated with inhibition of ovulation (either oral, injectable, or implantable) for at least 6 weeks prior to first dose of study intervention.
- 3. Intrauterine progestogen releasing system for at least 6 weeks prior to first dose of study intervention.
- 4. Bilateral tubal occlusion for at least 6 weeks prior to first dose of study intervention.
- 5. Combined (estrogen- and progestogen containing) hormonal contraception (either oral, intravaginal, or transdermal) for at least 6 weeks prior to first dose of study intervention.
- 6. Surgical sterilization of the male partner (medical assessment of azoospermia is required if vasectomy was performed within 6 months prior to first dose of study intervention). Male partner is still required to use condom during sexual intercourse.
- 7. Sexual abstinence for female participants:
  - a. Sexual abstinence is considered a highly effective method only if defined as refraining from heterosexual intercourse. In this study, abstinence is only acceptable if consistent with the participant's preferred and usual lifestyle. Abstinent female participants must refrain from heterosexual intercourse for at least 30 days after the final dose of study intervention.

Female participants must not donate ova from the Day 1 Visit at least until 30 days after their final dose of study intervention.

The following methods are considered unacceptable (not allowed) in this study:

- Periodic abstinence (calendar, symptothermal, or post-ovulation methods)

- Withdrawal (coitus interruptus)
- Spermicides only
- Lactational amenorrhea method
- Female condom and male condom should not be used together

## 10.5.2.2. Guidance for Male Participants

Contraception is the responsibility of the heterosexually active male participants in the study, regardless of his female partner's method of contraception.

Male participants who have had a vasectomy > 6 months prior to the first dose of study intervention must use a condom during heterosexual intercourse. Male participants who have had a vasectomy < 6 months prior to the first dose study intervention and those who have not had a vasectomy must use a condom (with or without spermicide) during heterosexual intercourse for at least 90 days (ie, 1 spermatogenesis cycle) after their final dose of study intervention.

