#### Table 5: Potential Risks and Mitigation Strategies

Potential Risk of Clinical Significance	Summary of Data/Rationale for Risk	Mitigation Strategy					
	Other						
Pregnancy exposure or lactation	No studies of ALXN2050 have been conducted in pregnant women. There are no data available on excretion of ALXN2050 in breast milk.	Pregnancy testing will be conducted as specified in the Schedule of Activities (SoA; Section 1.3). A negative serum pregnancy test (Screening Visit) and a negative urine pregnancy test (Day 1) are required prior to randomization. If a pregnancy is reported during the study, safety follow-up will be performed (Section 10.5.3). Pregnant or nursing women are excluded from participating in this clinical study. Participants and their spouses/partners must use a highly effective method of contraception during the study and for a period of 30 days following the final dose of study intervention					

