#### Sex

- 6. Male or female participant.
- 7. Female participants of childbearing potential and male participants must follow protocol-specified contraception guidance (Section 10.5.2).

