### 8.2.7. Pregnancy

A serum or urine pregnancy test will be administered to all female participants of childbearing potential. A negative serum pregnancy test at the Screening Visit and a negative urine pregnancy test at Day 1 are required in order to be considered eligible to continue in the study.

Pregnancy data from female participants and female spouses/partners of male participants will be collected from the first dose of study intervention and at the time points specified in the SoA (Section 1.3). Any female participant who becomes pregnant during the study will be

discontinued from the study intervention and withdrawn from the study. If a pregnancy is reported, the Investigator must immediately inform Alexion within 24 hours of awareness of the pregnancy and follow the procedures outlined in Section 10.5.3.

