## 10.5.2.2.1. Sexual Abstinence for Male Participants

Sexual abstinence is considered a highly effective method only if defined as refraining from heterosexual intercourse. In this study, abstinence is only acceptable if consistent with the participant's preferred and usual lifestyle. Abstinent male participants who become heterosexually active must use a condom and spermicide during intercourse.

Periodic abstinence (eg, calendar, symptothermal, or post ovulation methods for a female partner) is not considered a highly effective method of contraception for male participants.

Male participants must not donate sperm from the Day 1 Visit until 90 days after their final dose of study intervention.

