## **10.5.3.** Collection of Pregnancy Information

Pregnancy data will be collected during this study for all female participants, and female spouses/partners of male participants, from the first dose of study intervention until the last study visit. Any female participant who becomes pregnant during the study will be discontinued from the study intervention and withdrawn from the study. Exposure during pregnancy (also referred to as exposure in utero) can be the result of either maternal exposure or transmission of study intervention via semen following paternal exposure. If a female participant or a male participant's female spouse/partner becomes pregnant during the conduct of this study, the Investigator must submit the "Pregnancy/Breastfeeding Reporting and Outcome Form" to Alexion GDS via facsimile or email. When the outcome of the pregnancy becomes known, the form should be updated and submitted to Alexion GDS. If additional follow-up is required, the Investigator will be requested to provide the information.

Exposure of an infant to study intervention during breastfeeding must also be reported (via the "Pregnancy/Breastfeeding Reporting and Outcome Form") and any AEs experienced by the infant must be reported to Alexion GDS via email or facsimile.

Pregnancy is not regarded as an AE unless there is a suspicion that the study intervention may have interfered with the effectiveness of a contraceptive medication. However, complications of

pregnancy and abnormal outcomes of pregnancy are AEs and may meet the criteria for an SAE (eg, ectopic pregnancy, spontaneous abortion, intrauterine fetal demise, neonatal death, or congenital anomaly). Elective abortions without complications should not be reported as AEs.

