## 10.5.3.1. Male Participants with Partners Who Become Pregnant

- The Investigator will attempt to collect pregnancy information on any male participant's female partner who becomes pregnant while the male participant is in this study. This applies only to male participants who receive study intervention.
- After obtaining the necessary signed informed consent from the pregnant female partner directly, the Investigator will record pregnancy information on the appropriate "Pregnancy/Breastfeeding Reporting and Outcome Form" and submit it to Alexion within 24 hours of learning of the partner's pregnancy. The female partner will also be followed to determine the outcome of the pregnancy. Information on the status of the mother and child will be forwarded to Alexion. Generally, the follow-up will be no longer than 3 months following the delivery date. Any termination of the pregnancy will be reported regardless of fetal status (presence or absence of anomalies) or indication for the procedure.

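### Table 5 leaves out the 90-day male precautions, and the partner-pregnancy reporting window closes 58 to 62 days before those 90 days are over

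*Protocol*

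**What the plan says.** **Contraception after the last dose**

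- Table 5 (Potential Risks and Mitigation Strategies), in its pregnancy row, asks participants and their spouses or partners to use highly effective contraception during the study and "for a period of 30 days following the final dose of study intervention". It does not distinguish men from women and mentions no longer period.
- Section 10.5.2.1 sets the duration for women of childbearing potential: "until at least 30 days after the final dose of study intervention".
- Section 10.5.2.2 requires condom use by men with no vasectomy, or one less than 6 months before first dose, for "at least 90 days (ie, 1 spermatogenesis cycle" after the final dose. Men with an older vasectomy must also use a condom, but no post-dose duration is given for them.
- Section 10.5.2.2.1 applies to all men: "Male participants must not donate sperm from the Day 1 Visit until 90 days after their final dose of study intervention".
- Inclusion criterion 7 binds men to Section 10.5.2, not to Table 5.

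**Partner pregnancies**

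- Section 8.2.7 says pregnancy data from participants and partners "will be collected from the first dose of study intervention and at the time points specified in the SoA".
- Section 10.5.3 collects these data "from the first dose of study intervention until the last study visit". It also names transmission through semen as a route of exposure in pregnancy.
- Section 10.5.3.1 asks the investigator to attempt collection for a partner who "becomes pregnant while the male participant is in this study".
- The EOS Visit is the last visit (Section 4.1). It falls 30 (±2) days after the last dose (Section 4.1; Table 2, footnote a).

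**The concern.** The protocol treats the 90 days after a man's last dose as a period needing precaution. Two other parts of it stop at about day 30. The risk summary gives only the duration that applies to women, so someone who reads Table 5 alone would take 30 days as the whole post-dose requirement for men too. The partner-pregnancy rules also close about two thirds of the precaution period early.

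What is at stake is safety information. Table 5 itself says the drug has not been studied in pregnant women. If a partner conceives between the EOS Visit and day 90, nothing in the partner-pregnancy sections requires the pregnancy to be recorded or followed, and nothing visible tells the man to report it.

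**Working it through.** The documents state no figure for this gap, so there is none to reproduce. The check is a comparison of texts and day arithmetic.

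**Step 1. Durations side by side**

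| Text | Who | Obligation | Days after last dose |
|---|---|---|---|
| Table 5 | participants and partners | highly effective method | 30 |
| 10.5.2.1 | women of childbearing potential | highly effective method | at least 30 |
| 10.5.2.2 | men with no vasectomy, or one less than 6 months before first dose | condom | at least 90 |
| 10.5.2.2.1 | all men | no sperm donation | 90 |

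Table 5 matches the row for women. The two male rows have no counterpart in it. The longest male precaution exceeds the period shown in Table 5 by 90 − 30 = 60 days.

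**Step 2. Days outside the partner-pregnancy window**

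Inputs: a 90-day precaution period (10.5.2.2), and a last study visit on day 30 ± 2, that is, day 28 to day 32 (4.1; Table 2, footnote a).

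Days outside the window = 90 − EOS day:

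- EOS on day 28: 90 − 28 = 62 days; 62/90 = 69%
- EOS on day 30: 90 − 30 = 60 days; 60/90 = 67%
- EOS on day 32: 90 − 32 = 58 days; 58/90 = 64%

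**Step 3. Whether another route extends the window**

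- Section 10.3.1 requires pregnancies during maternal or paternal exposure to be reported within 24 hours of site awareness. It sets a deadline once the site knows. It creates no contact and no instruction to the man.
- Sections 8.3.1 and 10.3.4 deal with serious adverse events (SAEs) that a site learns of after participation ends, and 8.3.1 says sites need not look for them. Section 10.5.3 does not count a pregnancy as an adverse event unless interference with a contraceptive medication is suspected, so an uncomplicated partner pregnancy would ordinarily not qualify.
- Section 10.5.2 provides partner follow-up if teratogenic transfer is suspected, and refers to 10.5.3.1 for it.
- Section 10.5.3.2, on post-study pregnancy-related SAEs, belongs to the rules for female participants and again relies on spontaneous reports.

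None of these moves the end of the window.

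**Step 4. After the change**

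With the window extended to day 90, 90 − 90 = 0 days fall outside it. That describes the rule. Whether a given pregnancy is reported would still depend on the man telling the site.

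**The case against.** **Table 5 does not conflict with 10.5.2.2.** A reader might infer a contradiction, or that Table 5 understates the condom period by 60 days. The texts do not support that. Table 5 concerns a highly effective method, and condoms are not among the methods listed for women in 10.5.2.1. Section 10.5.2.2 is a condom rule that applies whatever the partner uses. A man can meet both, and criterion 7 sends him to 10.5.2. This part of the objection stands: the fault is an omission in a summary.

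**The window may be longer than day 30.** Section 10.5.3 also requires a form for pregnancies during the conduct of the study. Under Section 4.4 the study ends only with the last participant's last visit, so a trial-level reading would carry the duty past day 30 for many men. But 10.5.3.1, the section specific to partners, limits collection to the time that man is in the study, and 10.5.3 itself sets the last study visit as the end. The narrower text answers this reading, although the wording could be clearer.

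**Suspected teratogenic transfer.** Section 10.5.2 says that in such cases the partner is followed in the same way as a pregnant female participant, which could bring in follow-up to outcome under 10.5.3.2. That is a real provision, but it applies only once transfer is suspected.

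**Reporting during the study is also passive.** The Schedule of Activities has no row for partner pregnancy. Its pregnancy tests are for participants of childbearing potential, so reporting before EOS also relies on the site being told. This stands. The gap is therefore in the reporting window, and it would be too strong to say that scheduled monitoring stops at EOS.

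**No harm is shown.** The 90 days rest on a spermatogenesis cycle, whereas the exposure route named in 10.5.3 is drug in semen. Nothing says drug persists in semen through days 31 to 90. This also stands, and no such claim is made here.

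**Conclusion.** The point holds in two limited parts. Table 5 omits the 90-day condom period for men with no vasectomy or a recent one, and the 90-day sperm-donation ban for all men. It is incomplete and misleading as a summary, while the binding rule in 10.5.2 is intact. The partner-pregnancy window ends at the man's last study visit, so 58 to 62 days (64% to 69%) of the protocol's own 90-day period lie outside it, with only awareness-based routes left.

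The size rests on the stated visit window and on reading 10.5.3.1 as the operative limit for partners. For men with an older vasectomy, the condom comparison does not apply. The documents give no number of male participants or expected partner pregnancies, so no count of missed events can be given. The consent text is not available, so it cannot be said whether men are told there to report later pregnancies. No efficacy result, type I error rate or power is affected. It is a safety-consistency improvement worth making because it is cheap.

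**What to change.** 1. **Table 5.** Keep at least 30 days for women. Add at least 90 days of condom use for men with no vasectomy, or one less than 6 months before first dose, with a cross-reference to 10.5.2.2. An unrestricted 90 days of condom use for all men would go beyond 10.5.2.2 and create a new mismatch.
2. **Sections 10.5.3 and 10.5.3.1.** Extend the partner-pregnancy reporting window to conceptions up to 90 days after the man's last dose.
3. **EOS Visit.** Instruct men at this existing visit to report such pregnancies to the site.

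The cost is a few sentences and some reports to process after EOS. No new visit or call is required. Reporting would still rely on the man informing the site, but he would have been asked to do so and the site would have a clear duty to record what he reports.

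The SAP addendum records that the study was terminated. The 90 days run from each man's own last dose, and the documents do not say whether any man is still within them.
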